8.3.2 Analysis of Exploratory Data

For exploratory endpoint biomarkers other than microbiota 16S rRNA sequences, multivariate modification of cumulative incidence statistics of Fine and Gray will be used to evaluate the univariate and multiple effects of primary markers or secondary markers on endpoints. The cumulative incidence of primary endpoints of Grade III-IV GVHD at any time among all patients in the study will be based on the initial systemic diagnosis and treatment. Cox regression

analyses will be used to identify exploratory study parameters as risk factors for Grade III-IV GVHD. Exploratory assays with a P value $\leq .05$ for association with Grade III-IV GVHD in univariate testing will be entered in a multivariate Cox regression model.

Additionally, for each parameter, pairwise comparisons will be made between pre-transplant and each post-transplant time point. Statistical comparisons between GVHD(+) and GVHD(-) groups will be performed using a χ^2 or Fisher's exact test for categorical variables or the non-parametric Mann-Whitney U test for continuous variables. Mean values obtained from ELISA assays performed on pre- and post-transplant samples will be compared with the non-parametric Mann-Whitney U test for continuous variables. Next, the change in each blood factor at a given time relative to before the conditioning regimen was initiated will be compared using a paired t-test in GVHD (+) and GVHD (-) groups.

For 16S rRNA data, statistical analysis will follow the methods outlined above and detailed in Jenq et al. [99], briefly as follows:

Determining diversity, phylogenetic classification, dissimilarity, microbial chaos, and UniFrac PCoA. Operational Taxonomic Unit (OTU)-based microbial diversity will be estimated by calculating the Shannon diversity index ([Magurran, A.E. 2004. Measuring Biological Diversity. Blackwell Pub., Malden, Ma.2004](#)) using MOTHUR open software. Phylogenetic classification will be performed for each sequence, using the Bayesian classifier algorithm described (Wang, Q., G.M. Garrity, J.M. Tiedje, J.R. Cole. 2007. Naive Bayesian classifier for rapid assignment of rRNA sequences into the new bacterial taxonomy. *Appl. Environ. Microbiol.* 73:5261–5267. doi:10.1128/AEM.00062-07) with bootstrap cutoff at 60%. A phylogenetic tree will be inferred using clearcut on the 16S sequence alignment generated by MOTHUR. Microbial chaos is quantified by mean Bray-Curtis time index, calculated as follows: Bray-Curtis dissimilarity index ([Magurran, 2004](#)) between temporally adjacent samples will be quantified using MOTHUR and divided by the length of the time interval (in days) between samples, starting with the samples obtained before the transplant and all samples obtained until end of study. Unweighted UniFrac on the resulting tree (Lozupone, C., M. Hamady, R. Knight. 2006. UniFrac—an online tool for comparing microbial community diversity in a phylogenetic context. *BMC Bioinformatics.* 7:371. doi:10.1186/1471-2105-7-371) will be analyzed by Principal Coordinates Analysis performed on the resulting matrix of distances between each pair of samples.

Statistical comparisons. Shannon diversity index for intervals will be compared using unpaired two-sided Student's t tests with a more stringent cut-off of 0.0125 given multiple comparisons, by the Bonferroni correction for multiple time periods of independent comparisons. Comparisons of bacterial populations will use paired two-sided Wilcoxon matched pairs test for individual patients. Other comparisons will employ two-sided Mann-Whitney tests. However, given the final sample size (dependent on patient compliance with request for samples) rigorous statistical inference may be limited by confounding factors that can affect microbiome readouts in addition to GVHD. These include the exact combination and dosage of antibiotics, the underlying disease, patient nutrition, diarrhea, etc.. We will have to make this

assessment *post hoc*. It may be that, to avoid over-interpretation of data, we will limit the analysis to data description and visualization. This is acceptable for a pilot study.

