1.5 Biomarkers of GVHD as potential predictors of GVHD

1.5.1 Plasma proteins detected by Enzyme Linked Immunoassay (EIA)

Progress has been made in identifying blood markers of GVHD [83-87]. Levine et al. [83] showed that a panel of 6 plasma markers (elafin, IL-8, TNFR1, HGF, reg3a, IL-2Ra) significantly correlated with non-responsive GVHD and non-relapse mortality (NRM). More recently, the same group, using a more extensive panel, partially overlapping with their previous one, found that essentially **full predictive power was provided by a single marker, ST2** (suppression of tumorigenicity 2), a recently described member of the IL-1R family, which binds IL-33, thereby driving T cells toward a Th1 effector phenotype [86, 87]. High ST2 levels in the first two weeks post-HCT were strongly predictive of non-relapse mortality (NRM) in patients with IT GVHD, but not with skin GVHD only. The Paneth cell regeneration marker, **reg3a, had independent and additive predictive value for IT GVHD** [88]. This is consistent with very recent findings from models showing that early immune mediated destruction of paneth cells in the intestinal villous crypts eliminates their production of beneficial alpha-defensins, leading, in turn, to altered gut flora, with overgrowth by *E. coli*, *C. difficile*, seeding of organs, and septic complications causing death [88-92]. In a somewhat analogous, but converse manner, Levine et al. found that plasma elafin levels rose at the onset of skin GVHD, but not IT GVHD, and were predictive of NRM [83]. By contrast with elafin or reg3a and ST-2, ceruloplasmin plasma levels between days 7 - 28 post-HCT were highly significant predictors of *both* skin and IT GVHD [93].

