3.3 Exploratory Objectives

- 3.3.1 To identify biomarkers that correlate with, or are predictive of, grade III-V GVHD
- 3.3.2 To identify gut and urine flora diversity (Shannon Diversity Index) and changes in the percentages of firmicutes, bacteroidetes, and enterocci, ratio of Clostridia and Lactobacillus species over time, pre- and post- transplantation, in the presence and absence of telmisartan and/or GVHD. The healthy microbiome contains 40-50% firmicutes, 30-40% bacteroidetes, and < 10% enterocci. Some dysbiosis occurs as a result of conditioning and transplantation, with enterocci increasing to ~ 25%. However, during GVHD, these ratios change dramatically, with enterocci increasing to ~50%, and bacteroidetes dramatically dropping.
- 3.3.3 To assess the level of ROCK activity in peripheral blood mononuclear cells, on and off telmisartan treatment, in the presence or absence of GVHD.
- 3.3.4 To measure percentages of lymphocyte subsets, described above, associated with GVHD or suppression of GVHD.

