4.0 STUDY POPULATION

The study population will consist of 60 patients undergoing allogeneic HCT for treatment of hematologic malignancies meeting the following criteria. Subject eligibility will be documented by a qualified member of the study team.

4.1 Eligibility Criteria:

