8.3 Statistical Analysis Plan

8.3.1 Efficacy Endpoints for Grade III-IV and Grade II GVHD.

The statistical test used for endpoints (Z test of proportions) takes the currently available 3 year JTCC data as the historical control data set for comparison. In reviewing these data, as currently available, it appears that the JTCC rates of severe GVHD, NRM, and cancer relapse are somewhat lower (i.e. better patient outcomes) than the national averages from published studies. For our final determinations of significance, we will use updated JTCC 3 year data as they become available at time of study completion.

Outcome variables examined include engraftment, GVHD, relapse, and NRM, however the efficacy hypotheses are constructed in relation to GVHD only.

Primary endpoint analysis

Historic GVHD data are available on 178 allogeneic transplants, of whom 46 (26%) experienced grade III or IV acute GVHD. All the other allogeneic transplantees (74%) had grade II GVHD. Based on these data, if 8 or fewer of the total 60 study participants experience grade III - IV acute GVHD during the course of the study, we will have demonstrated a protective effect for this criterion, with a $p < 0.05$, based on a one-way Z test for a decreased proportion.

Sample Size and Power Calculation Considerations

If we use the proportion $P=0.26$ as the rate of Grade III - IV GVHD in the current standard treatment, then using a one-sided exact test of the proportion and significance level of 0.05, testing if 9/60 (15%) rate of Grade III-IV GVHD is achievable with telmisartan treatment will have 58.8% power to detect this effect, if it exists. Testing for a 12% rate would achieve 82.2% power. Using the recommended level of significance, 0.025, for a one-sided test, testing if the grade III-IV GVHD by day 100 is 0.15, would have power of 44.4% of detecting this effect. At the 2.5 % level, testing if the rate is less than 0.11, will have 79.0 % power of detecting. Testing if the rate of grade III-IV in telmisartan treated transplantees is 0.10, will have 85.8% power of detecting this effect using the 2.5 % level of significance.

Numeric Results for testing $H_0: P = P_0$ versus $H_1: P < P_0$ using the PASS13 sample size software Test Statistic: Exact Test

Power	N	Proportion		Target Alpha	Actual Alpha	Beta	Reject H_0 If $R \leq$ This
		Given H_0 (P_0)	Given H_1 (P_1)				
0.8584	60	0.2600	0.1000	0.0250	0.0140	0.1416	8
0.7899	60	0.2600	0.1100	0.0250	0.0140	0.2101	8

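### The biomarker Cox model admits every assay with univariate p ≤ .05, with about 6 to 16 events, no cap or shrinkage, and no rule on which serial sample is used

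*Combined protocol and SAP*

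**What the plan says.** Section 8.3.2 covers the exploratory biomarkers other than the microbiome. It first names the Fine and Gray approach for single and joint marker effects. The outcome is described as "The cumulative incidence of primary endpoints of Grade III-IV GVHD at any time among all patients in the study". It then turns to Cox regression for risk factors for grade III-IV GVHD, and assays that reach p ≤ .05 "in univariate testing will be entered in a multivariate Cox regression model".

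For these markers the section gives no maximum number of covariates, multiplicity control, shrinkage or internal validation. It does not say whether the baseline value, a fixed-day value, a peak or the latest value enters the model, and it mentions neither a landmark nor time-dependent covariates. Serial measurement is dealt with only outside the Cox model, by pre/post and group comparisons.

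The objective in Section 3.3 is "To identify biomarkers that correlate with, or are predictive of, grade III-V GVHD".

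**The concern.** Two features of the rule work against a predictive claim.

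**Selection with few events.** Markers are chosen by p-value and then fitted together without penalty, on an outcome that few of the 60 patients will have. Estimates for selected markers are then biased away from the null, and null markers can be retained.

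**Timing.** Blood is drawn before transplant and repeatedly afterwards (Table 3, Section 6.5.1). Section 5.3.5 keeps patients with GVHD on study and has those at grade II or above treated with systemic corticosteroids, so later values can reflect existing disease and its treatment. Late samples also exist only for survivors: Section 8.4 expects 15% non-relapse mortality by Day 100, or 0.15 × 60 = 9 patients. Without a timing rule, a marker of established GVHD can be reported as a risk factor for it.

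At stake is the use that Section 2.0 foresees for confirmed markers, which is to guide the timing of immune suppression in future patients.

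**Working it through.** **Inputs from the documents**
- Sample size (Section 4.0): "The study population will consist of 60 patients undergoing allogeneic HCT".
- Historical rate (Section 8.3.1): "Historic GVHD data are available on 178 allogeneic transplants, of whom 46 (26%) experienced grade III or IV acute GVHD".
- Success boundary (Section 8.3.1): "if 8 or fewer of the total 60 study participants experience grade III - IV acute GVHD". The closing summary of that section says 7, which makes no difference here.
- Design alternative (Section 8.3.1): "Testing if the rate of grade III-IV in telmisartan treated transplantees is 0.10, will have 85.8% power". A rate of 0.11 is also tabulated.
- Screening threshold (Section 8.3.2): univariate p ≤ .05.
- Candidate markers (Section 5.2.3): ST2, reg3a, ceruloplasmin, elafin and endotoxin activity (5); the ROCK phosphorylation ratio and ROCK protein level (2); lymphocyte subsets (about 7). The total is about 14, or 12 to 15 depending on how the subsets are counted.

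**The plan's own figures.** Exact binomial with N = 60 and boundary 8: P(X ≤ 8 | 0.26) = 0.0140, P(X ≤ 8 | 0.10) = 0.8584 and P(X ≤ 8 | 0.11) = 0.7899. All three match the table. No event count or power is stated for the biomarker model.

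**Expected events = 60 × rate**
- Historical 26%: 60 × 0.26 = 15.6.
- Success boundary: at most 8.
- Alternatives of 11% and 10%: 60 × 0.11 = 6.6 and 60 × 0.10 = 6.0.

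**False entries, each of k markers tested once, all null and independent.** Expected number = 0.05k; chance of at least one = 1 − 0.95^k.

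| k | Expected false entries | Chance of at least one |
|---|---|---|
| 12 | 0.60 | 46% |
| 13 | 0.65 | 49% |
| 15 | 0.75 | 54% |

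**What selection does to the estimates.** A simulation took 60 patients, 13 independent null markers, and onsets spread evenly over days 10 to 100. Markers were screened one at a time by a Cox score test and those that passed were refitted together. At least one null marker passed in 49% of runs with 8 events and 50% with 16. The median apparent hazard ratio per SD among those that passed, taken in whichever direction exceeds 1, was 2.3 with 8 events and 1.8 with 16. The true value was 1.0.

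**What the events can support.** For one pre-specified continuous marker, the hazard ratio per SD detectable with 80% power at two-sided 0.05 is exp[(1.960 + 0.842)/√events]: 2.0 with 16 events, 2.7 with 8 and 3.1 with 6. Two covariates leave 3 to 8 events each, and three leave 2 to 5.3. Under an assumed rule of thumb of 10 events per covariate, 6 to 16 events support no more than one unpenalised covariate.

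**The case against.** The analysis is exploratory, in a pilot. Sections 6.5 and 7.3 say that its results will not guide patient care, and Section 2.0 already accepts that an effective drug leaves fewer events to correlate. Fine and Gray is named, so competing events are considered. All of this stands and limits the weight of the point. It does not answer it: Fine and Gray addresses neither overfitting nor the timing of covariates, and its relation to the Cox model is not explained. The Bonferroni cut-off and the fallback to description in Section 8.3.2 concern the microbiome data only.

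A reader might infer more than the documents support.

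- *That every assay is screened at every visit.* With 13 assays and four visits there would be 52 tests, 52 × 0.05 = 2.6 false entries and, at 8 events, about 3 events per false covariate. But the text screens assays, not assay-by-visit pairs, and the four visits would be an assumption. Sampling is also not uniform: Section 6.5.1 limits endotoxin samples to visits before Day +56, and Section 1.7 plans ROCK at baseline, three times on drug and twice after. More tests would result only if visits were screened separately.
- *That post-onset values will be used.* The plan is silent, and pre-transplant samples are collected. In a simulation that treated a null marker's highest value up to the event as a baseline value, 62% of tests with 16 events were falsely positive. That is a worst case, and the plan does not specify peak values.
- *That the stated aim would fail.* Section 3.3 accepts markers that correlate with GVHD or predict it. Correlation can still be examined; only the predictive half is at risk.

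**Conclusion.** The point holds as a gap in specification combined with a weak selection rule. With 6 to 16 events, and a 46% to 54% chance that at least one null marker enters, a multivariable model chosen at p ≤ .05 cannot reliably support a claim that a marker predicts grade III-IV GVHD. Without a timing rule it also cannot separate prediction from detection. The primary efficacy test and patient management are untouched, so this is an inexpensive improvement to an exploratory analysis.

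The figures assume one test per marker, independent null markers (positive correlation would lower the chance of at least one false entry), and 12 to 15 markers by count. The sentence that defines the outcome window refers to cumulative incidence; it is read here as also covering the Cox outcome, with time measured from transplant. How many markers would actually enter is unknown, so overfitting is likely but not certain.

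**What to change.** Amend Section 8.3.2 as follows.

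1. **Timing.** In the Cox and Fine-Gray marker models, use only values drawn before GVHD onset, and state which grade defines onset. Either enter them as time-dependent covariates in the Cox model, which keeps early onsets, or take them from a stated landmark day and count only later onsets.
2. **Multivariable model.** Replace the p ≤ .05 entry rule with a Firth-penalised model of at most two markers, named before the batch assays are run. ST2 and reg3a are candidates: Section 1.5.1 reports that reg3a "had independent and additive predictive value for IT GVHD". That section ties ST2 to non-relapse mortality in intestinal GVHD and reg3a to intestinal disease, whereas it supports ceruloplasmin for both skin and gut. The choice should therefore be argued against the grade III-IV outcome. Penalisation is needed even with two markers, given 3 to 8 events each.
3. **Other assays.** Report them one at a time, labelled hypothesis-generating, with the number of tests and a false-discovery-rate adjustment.
4. **Event count.** State the expected number of events beside the model.

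The cost is SAP wording and slightly more analysis work, with no new samples, visits or patients. If a landmark is used, patients with earlier onset drop out of that model, which reduces an already small event count.

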5.2.3 Exploratory Endpoints

- ST2 EIA (Presage, Critical Diagnostics)
- Reg3a EIA
- Ceruloplasmin EIA
- elafin EIA
- endotoxin activity assay (EAA, Spectral Diagnostics)
- Gut and urine microbiome sequencing of 16S rRNA DNA, to generate Shannon Diversity index and ration of Clostridia : Lactobacilli, and *firmicutes* vs. *bacteroidetes* vs. *Enterococci* species
- PBMC ROCK activity as measured by ratio of Phosphorylated : Total MBS in cryopreserved PBMCs, ROCK enzyme protein levels by WB
- Percentages of CD4+ and CD8+ cells expressing FoxP3 and CD73 or CD39, percentages of CD4+ CD146+CCR5+ cells, and percentages of a4b7 cells expressing CD39 or CD73.

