6.5.2 Stool and Urine Samples

Stool and clean-catch urine samples for microbiome analysis will be collected twice between Day -5, and Day 0, again on Day +7, and all subsequent clinic visits until Day +100, and once more on day 180. Kits for stool and urine collection will be provided to subjects prior to each visit. While all attempts should be made to collect these samples at all required time points, a subject can

forego collection at an individual collection if they cannot provide a stool or urine sample due to decreased performance status, malnutrition/dehydration, or other medical reasons.

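### Shannon diversity is compared by unpaired t tests although patients are sampled repeatedly and no rule gives one value per patient; the 0.0125 cut-off cannot be verified because its comparisons are not listed

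*Combined protocol and SAP*

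**What the plan says.** Section 5.2.3 makes Shannon diversity an exploratory endpoint in two specimens: "Gut and urine microbiome sequencing of 16S rRNA DNA, to generate Shannon Diversity index". Section 6.5.2 collects stool and urine twice before transplant, then "again on Day +7, and all subsequent clinic visits until Day +100, and once more on day 180". Patients may skip a collection for medical reasons.

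For the analysis, Section 8.3.2 first gives a general rule: "for each parameter, pairwise comparisons will be made between pre-transplant and each post-transplant time point". It then says: "For 16S rRNA data, statistical analysis will follow the methods outlined above", and adds that details are in a cited microbiome study. The rule specific to diversity compares intervals by unpaired, two-sided t tests "with a more stringent cut-off of 0.0125 given multiple comparisons, by the Bonferroni correction for multiple time periods of independent comparisons".

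The section does not say how many intervals there are, where they begin and end, or whether the contrast is between intervals or between patients with and without GVHD. It does not say whether stool and urine share one error family, or how several samples from one patient in one interval are handled. The next sentence of the plan uses a paired Wilcoxon test for bacterial populations within patients. The section ends by allowing that the microbiome analysis may be reduced to description and visualization.

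**The concern.** An unpaired t test assumes that every observation, in both groups, comes from a different patient. The schedule does not deliver that. An interval covering Days +7 to +28 could hold four samples from one patient, and one covering Days +70 to +100 could hold three. Two intervals compared with each other contain largely the same patients.

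These two departures act in opposite directions. Pooling several samples per patient in a between-group test overstates the information and inflates false positives. Ignoring the pairing in a within-patient test overstates the standard error and hides real change. Under either, the p-value does not have the size that the 0.0125 threshold implies.

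Section 7.3 says the trial will test whether diversity falls in association with GVHD. A reader who sees a Bonferroni-corrected threshold met will take the finding as protected against chance. If the intervals, contrast and family are settled only after the data are seen, that protection is weaker still.

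**Working it through.** **Inputs from the documents.** 60 evaluable patients (Section 5.5.2); repeated stool and urine samples (Section 6.5.2 and Tables 3 and 3A); per-test cut-off 0.0125, two-sided, unpaired (Section 8.3.2).

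**Assumptions.**
- Constant within-patient correlation ρ of 0.3, 0.5 or 0.7 between samples. The documents give no value.
- GVHD groups of 16 and 44, from 0.26 × 60 = 15.6, using the historical grade III-IV rate in Section 8.3.1.
- Three or four samples per patient per interval.

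**The plan's own figure.** 0.05/4 = 0.0125 exactly, so the cut-off is Bonferroni for four comparisons if the family level is 0.05. The plan does not state a family level for this analysis.

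**Between-group test with pooled samples.** With k samples per patient entered as separate observations, the variance of a group mean is larger than the t test assumes by the factor 1 + (k − 1)ρ. The two-sided critical value at 0.0125 is z = 2.498, so approximately

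true size = 2 × [1 − Φ(2.498 / √(1 + (k − 1)ρ))].

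| k | ρ | variance factor | 2.498/√factor | true size | simulated |
|---|---|---|---|---|---|
| 3 | 0.3 | 1.6 | 1.975 | 4.8% | 4.8% |
| 3 | 0.5 | 2.0 | 1.766 | 7.7% | 8.0% |
| 3 | 0.7 | 2.4 | 1.612 | 10.7% | 10.9% |
| 4 | 0.3 | 1.9 | 1.812 | 7.0% | 7.2% |
| 4 | 0.5 | 2.5 | 1.580 | 11.4% | 11.9% |
| 4 | 0.7 | 3.1 | 1.419 | 15.6% | 16.1% |

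The simulation used 40,000 runs per correlation. With each patient's mean in place of the separate samples, the same simulation gives 1.3% to 1.4%, close to the nominal 1.25%.

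**Interval versus interval in the same patients.** With one sample per patient per interval, the variance of the mean difference is smaller than the unpaired test assumes by the factor 1 − ρ, so

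true size = 2 × [1 − Φ(2.498 / √(1 − ρ))].

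- ρ = 0.3: 2.498/0.837 = 2.985, size 0.28%.
- ρ = 0.5: 2.498/0.707 = 3.532, size 0.04%.
- ρ = 0.7: 2.498/0.548 = 4.560, size below 0.001%.

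For a shift of 0.4 SD in 60 patients (an illustrative value), simulated power at 0.0125 is:

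| ρ | unpaired | paired |
|---|---|---|
| 0.3 | 34% | 52% |
| 0.5 | 32% | 70% |
| 0.7 | 28% | 92% |

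**Does dependence between the comparisons harm the correction itself?** No. With four between-group comparisons at 0.0125 and one value per patient per interval, simulated family-wise error is 4.1% to 4.9% for ρ from 0 to 0.6. With three samples per patient pooled, the same four comparisons give 14.6% at ρ = 0.3 and 19.7% at ρ = 0.6. The damage comes from the pooled test, not from the Bonferroni step.

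**The case against.** The strongest reply is that the plan never says samples will be pooled. It is silent on how an interval is formed, and silence is not a decision to enter each sample separately. The interval definition may lie in the cited microbiome study, which is not available here. This stands: the 5% to 16% range is conditional on pooling and on assumed correlations. It does not remove the need for a rule, because the text as written allows pooling, and the other natural use of the test (interval against interval) is also mis-sized.

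The endpoint is exploratory, guides no patient's care (Section 6.5), and the plan already warns against over-interpretation. This also stands, and it limits the severity. The fallback to description does not settle the matter, because that choice is left until after the data are in.

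Two stronger readings are tempting, and the documents support neither.

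- **That the plan makes eight or more comparisons, so 0.0125 is wrong.** A reader might multiply four intervals by two specimens to get eight, or expand the weekly visits to 12 post-transplant dates and double them to get 24. At 0.0125 the family-wise bounds would then be 8 × 0.0125 = 10% and 24 × 0.0125 = 30%. But the diversity rule speaks of intervals, not visits, and four intervals would match the cut-off exactly. Eight requires stool and urine to be one error family, which the plan does not say and on which statisticians reasonably differ.
- **That repeated sampling breaks the Bonferroni correction.** Bonferroni holds under any dependence. Calling the comparisons independent is a poor description, but the correction does not rely on it.

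**Conclusion.** The concern holds as a point about the test, not about the correction. Section 8.3.2 prescribes an unpaired t test for data sampled repeatedly from the same patients and gives no step that yields one value per patient. For within-patient correlation of 0.3 to 0.7, a test of GVHD against no GVHD that pools three or four samples per patient has a true size of about 5% to 16% at a nominal 1.25%. An unpaired comparison of intervals in the same patients has a size of 0.3% or less, with power of 28% to 34% against 52% to 92% for a paired test at a 0.4 SD shift.

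These figures rest on assumed correlations, an assumed 16 to 44 split and an assumed number of samples per interval. The direction of each effect needs only positive within-patient correlation.

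The 0.0125 cut-off is arithmetically 0.05/4 but cannot be verified, because the comparisons it covers are not listed. Severity is minor: the endpoint is exploratory and no trial decision rests on it.

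**What to change.** In Section 8.3.2:

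1. Define the intervals by study day and state the contrasts: GVHD against no GVHD within an interval, interval against interval, or both.
2. Reduce each patient's samples in an interval to one Shannon value, the patient's mean, separately for stool and urine.
3. Use an unpaired test between GVHD groups and a paired test between intervals. Alternatively, fit one mixed model with a patient random effect, which also copes with skipped samples.
4. State whether stool and urine form one error family. Set the cut-off to 0.05/k, or use Holm, for the k comparisons listed. If k is four, 0.0125 stands. If four intervals in two specimens are one family, it becomes 0.05/8 = 0.00625.
5. Or state now that the microbiome p-values are descriptive and drop the corrected threshold. Steps 1 to 3 are still worth keeping.

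The cost is wording only, with no new samples or patients. A larger k would take some power from an exploratory test; the paired test gives power back for within-patient change.
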